### **7.2.1. Withdrawal of Consent**

Participant's parent(s)/legal guardian(s) who request to discontinue receipt of study intervention will remain in the study and must continue to be followed for protocol-specified follow-up procedures. The only exception to this is when a participant's parent(s)/legal guardian(s) specifically withdraws consent for any further contact with him or her or persons previously authorized by the participant to provide this information. Participant's parent(s)/legal guardian(s) should notify the investigator in writing of the decision to withdraw consent from future follow-up, whenever possible. The withdrawal of consent should be explained in detail in the medical records by the investigator, as to whether the withdrawal is only from further receipt of study intervention or also from study procedures and/or posttreatment study follow-up, and entered on the appropriate CRF page. In the event that vital status (whether the participant is alive or dead) is being measured, publicly available information should be used to determine vital status only as appropriately directed in accordance with local law.

### **7.3. Lost to Follow-up**

A participant will be considered lost to follow-up if he or she repeatedly fails to return for scheduled visits and the participant's parent(s)/legal guardian(s) is unable to be contacted by the study site.

The following actions must be taken if a participant fails to return to the clinic for a required study visit:

- The site must attempt to contact the participant's parent(s)/legal guardian(s) and reschedule the missed visit as soon as possible and counsel the participant's parent(s)/legal guardian(s) on the importance of maintaining the assigned visit schedule and ascertain whether or not the participant's parent(s)/legal guardian(s) wishes the participant to, and/or should, continue in the study;

- Before a participant is deemed lost to follow-up, the investigator or designee must make every effort to regain contact with the participant's parent(s)/legal guardian(s) (where possible, 3 telephone calls and, if necessary, a certified letter to the participant's last known mailing address or local equivalent methods). These contact attempts should be documented in the participant's medical record;
- Should the participant's parent(s)/legal guardian(s) continue to be unreachable, the participant will be considered to have been withdrawn from the study.

Discontinuation of specific sites or of the study as a whole is handled as part of [Section 10.1 \(Appendix 1\)](#).

## **8. STUDY ASSESSMENTS AND PROCEDURES**

The investigator (or an appropriate delegate at the investigator site) must obtain a signed and dated ICD before performing any study-specific procedures.

The date of birth will be collected to critically evaluate the immune response and safety profile by age.

Study procedures and their timing are summarized in the [SoA](#). Protocol waivers or exemptions are not allowed.

Safety issues should be discussed with the sponsor immediately upon occurrence or awareness to determine if the participant should continue or discontinue study intervention.

Adherence to the study design requirements, including those specified in the [SoA](#), is essential and required for study conduct.

All screening evaluations must be completed and reviewed to confirm that potential participants meet all eligibility criteria. The investigator will maintain a screening log to record details of all participants screened and to confirm eligibility or record reasons for screening failure, as applicable.

Every effort should be made to ensure that protocol-required tests and procedures are completed as described. However, it is anticipated that from time to time there may be circumstances outside the control of the investigator that may make it unfeasible to perform the test. In these cases, the investigator must take all steps necessary to ensure the safety and well-being of the participant. When a protocol-required test cannot be performed, the investigator will document the reason for the missed test and any corrective and preventive actions that he or she has taken to ensure that required processes are adhered to as soon as possible. The study team must be informed of these incidents in a timely manner.

For samples being collected and shipped, detailed collection, processing, storage, and shipment instructions and contact information will be provided to the investigator site prior to initiation of the study.

The total blood sampling volume for individual participants in this study is approximately 15 mL.

## 8.1. Immunogenicity Assessments

### 8.1.1. Immunogenicity Assessments

Blood samples (approximately 5 mL per sample) will be collected from all participants at Visit 4 (1 month after Dose 3), Visit 5 (prior to administration of Dose 4), and Visit 6 (1 month after Dose 4). These are the immunogenicity time points.

#### 8.1.1.1. Pneumococcal Responses

##### IgG Responses to the 20 Serotypes Contained in 20vPnC

IgG antibody concentrations for serotypes present in 20vPnC (1, 3, 4, 5, 6A, 6B, 7F, 8, 9V, 10A, 11A, 12F, 14, 15B, 18C, 19A, 19F, 22F, 23F, and 33F) will be determined on all sera collected at the 3 immunogenicity time points (Visits 4, 5, and 6). The serotype-specific IgG concentrations will be measured by Pfizer's multiplex Luminex immunoassay.

##### OPA Responses to the 20 Serotypes Contained in 20vPnC

OPA titers for serotypes present in 20vPnC (1, 3, 4, 5, 6A, 6B, 7F, 8, 9V, 10A, 11A, 12F, 14, 15B, 18C, 19A, 19F, 22F, 23F, and 33F) will be determined in selected subsets of sera for the immunogenicity time points (Visits 4, 5, and 6). These subsets will be randomly selected, by an unblinded third party, to assure that each subset has equal representation of all vaccine groups. Further details will be described in the CSAP.

CCI [REDACTED]

CCI [REDACTED]

CCI [REDACTED]

CCI

## 8.2. Safety Assessments

A clinical assessment, including medical history and measurement of axillary temperature, will be performed on all participants prior to vaccination to determine participant eligibility and to establish a clinical baseline. Significant medical history and significant findings from any physical examination (if performed) will be recorded as medical history in the CRF. Temperature measurement prior to vaccination will be documented and recorded in the CRF.

The participant will be observed for 30 minutes after each study vaccination and any reactions occurring during that time will be recorded as AEs.

Prompted e-diary events, including local reactions (redness, swelling, and pain at the injection site) and systemic events (fever, decreased appetite, drowsiness/increased sleep, and irritability) that occur 7 days after investigational product administration (Days 1 through 7, where Day 1 is the day of vaccination), are graded as described in [Section 8.2.2.1](#) and [Section 8.2.2.2](#). Furthermore, AEs, SAEs, and NDCMCs will be collected as defined in [Section 10.3](#).

Planned time points for all safety assessments are provided in the [SoA](#). Unscheduled clinical laboratory measurements may be obtained at any time during the study to assess any perceived safety concerns.

### 8.2.1. Participant Electronic Diary

The participant's parent(s)/legal guardian(s) will be asked to monitor and record local reactions, specific systemic events, and antipyretic/pain medication taken for 7 days, each evening, following each administration of investigational product (20vPnC or 13vPnC) using an e-diary (in a provisioned device or application on a personal device). This allows recording of these assessments only within a fixed time window, thus providing the accurate representation of the participant's experience. Data on local reactions, specific systemic events, and antipyretic/pain medication reported in the e-diary will be transferred electronically to the e-diary vendor, where they will be available for review by investigators, their qualified designees, and sponsor staff at all times via an internet-based portal. At intervals agreed to by the vendor and Pfizer, these data will be transferred electronically to Pfizer for analysis and reporting.

The daily e-diary data will not be captured in the CRF. However, if a participant is withdrawn because of prompted events reported in the e-diary, the event(s) should be recorded on the AE page of the CRF, regardless of whether the investigator considers the event(s) to be clinically significant.

The investigator or designee must obtain stop dates for any local reactions or specific systemic events on the last day that the e-diary was completed. The stop dates should be entered in the CRF.

Investigators (or an appropriately qualified designee) are required to review the e-diary data online at frequent intervals (daily is optimal) to evaluate participant compliance and reported events as part of the ongoing safety review.

### **8.2.2. Grading Scale for Prompted Events**

The grading scales used in this study to assess prompted events as described below are based on concepts outlined in the FDA CBER guidelines on toxicity grading scales for adults and adolescent volunteers enrolled in preventive vaccine clinical trials, but have been adapted for applicability to healthy infants.

#### **8.2.2.1. Local Reactions**

For the first 7 days following each study vaccination (Days 1 through 7, where Day 1 is the day of vaccination), the participant's parent(s)/legal guardian(s) will be asked to assess redness, swelling, and pain at the 20vPnC or 13vPnC injection site (anterolateral thigh) and to record the symptoms in the e-diary in the evening. Redness and swelling will be measured and recorded in measuring device (caliper) units (range: 1 to >14; an entry in the e-diary of 15 will denote >14), and then categorized during analysis as mild, moderate, or severe based on the grading scale in [Table 2](#). Measuring device units can be converted to centimeters according to the following scale: 1 measuring device unit = 0.5 cm. Pain at the vaccine injection site will be assessed by the participant's parent(s)/legal guardian(s) as mild, moderate, or severe according to the grading scale in [Table 2](#). The participant's parent(s)/legal guardian(s) will be prompted to contact the investigator if the participant experiences a severe (Grade 3 or above) local reaction to assess the reaction and perform an unscheduled assessment or visit as appropriate.

Only an investigator is able to classify a participant's local reaction as Grade 4, after physical examination of the participant or documentation from another medically qualified source (eg, emergency room or hospital record). If a participant experiences a Grade 4 local reaction, the investigator must immediately notify the sponsor. Site staff will educate the participant's parent(s)/legal guardian(s) regarding signs and symptoms that would prompt site contact.

The procedure for notification of the sponsor is provided in the ISF or equivalent.

**Table 2. Grading Scales for Local Reactions**

Local Reaction	Grade 1 (Mild)	Grade 2 (Moderate)	Grade 3 a (Severe)	Grade 4 b
Redness	1 to 4 caliper units (or measuring device units) = >0 to 2.0 cm	5 to 14 caliper units (or measuring device units) = >2.0 to 7.0 cm	>14 caliper units (or measuring device units) = >7 cm	Necrosis or exfoliative dermatitis
Swelling	1 to 4 caliper units (or measuring device units) = >0 to 2.0 cm	5 to 14 caliper units (or measuring device units) = >2.0 to 7.0 cm	>14 caliper units (or measuring device units) = >7 cm	Necrosis
Pain at injection site (tenderness)	Hurts if gently touched (eg, whimpers, winces, protests, or withdraws)	Hurts if gently touched with crying	Causes limitation of limb movement	Emergency room visit or hospitalization for severe pain (tenderness) at injection site

Abbreviation: CRF = case report form.

Note: If the size of the redness and/or swelling falls between 2 measuring device units, the higher measuring device unit number will be recorded in the e-diary.

- a. Parents/legal guardians of the participants experiencing local reactions >14 caliper units (>7.0 cm) are to be contacted by the study site. An unscheduled visit may be required.
- b. Grade 4 assessment should be made by the investigator. Grade 4 will not be collected in the e-diary but will be collected as an AE on the CRF. The severity of the local reaction should be graded using the AE grading scale.

### 8.2.2.2. Systemic Events (Systemic Symptoms and Fever)

For the first 7 days following each study vaccination (Days 1 through 7, where Day 1 is the day of vaccination), the participant's parent(s)/legal guardian(s) will be asked to assess decreased appetite, drowsiness/increased sleep, and irritability and to record the symptoms in the e-diary (in a provisioned device or application on a personal device) in the evening. The symptoms will be assessed by the participant's parent(s)/legal guardian(s) as mild, moderate, or severe according to the grading scale in Table 3. The participant's parent(s)/legal guardian(s) will also be instructed to contact site staff if the participant experiences any possible Grade 4 prompted systemic event (ie, emergency room visit or hospitalization for severe decreased appetite, severe drowsiness/increased sleep, or severe irritability) within 7 days after vaccination. Study staff may also contact the participant's parent(s)/legal guardian(s) to obtain additional information on Grade 3 events entered into the e-diary.

Only an investigator is able to classify a participant's systemic event as Grade 4, after physical examination of the participant or documentation from another medically qualified source (eg, emergency room or hospital record) or telephone contact with the participant's parent(s)/legal guardian(s). If a participant experiences a Grade 4 systemic event, the investigator must immediately notify the sponsor.

The procedure for notification of the sponsor is provided in the ISF or equivalent.

**Table 3. Grading Scales for Systemic Event Symptoms**

Systemic Event	Grade 1 (Mild)	Grade 2 (Moderate)	Grade 3 (Severe)	Grade 4 a
Decreased appetite (loss of appetite)	Decreased interest in eating	Decreased oral intake	Refusal to feed	Emergency room visit or hospitalization for severe decreased appetite (loss of appetite)
Drowsiness (increased sleep)	Increased or prolonged sleeping bouts	Slightly subdued interfering with daily activity	Disabling not interested in usual daily activity	Emergency room visit or hospitalization for severe drowsiness (increased sleep)
Irritability (fussiness)  (synonymous with restless sleep; decreased sleep)	Easily consolable	Requiring Increased attention	Inconsolable; crying cannot be comforted	Emergency room visit or hospitalization for severe irritability (fussiness)

Abbreviations: CRF = case report form.

- a. Grade 4 assessment should be made by the investigator. Grade 4 will not be collected in the e-diary but will be collected as an AE on the CRF. The severity of the systemic event should be graded using the AE severity grading scale.

### 8.2.2.2.1. Fever

In order to record information on fever, a digital thermometer will be given to the participant's parent(s)/legal guardian(s) with instructions on how to measure axillary temperature at home. Temperature will be collected in the evening, daily, for 7 days following each study vaccination (Days 1 through 7, where Day 1 is the day of vaccination) and at any time during the 7 days that fever is suspected. Fever is defined as an axillary temperature of  $\geq 37.5^{\circ}\text{C}$ . The highest temperature for each day will be recorded in the e-diary. In the event of a fever on Day 7, temperature will be collected daily until fever has resolved (1 day of temperature  $< 37.5^{\circ}\text{C}$ ) in order to collect a stop date in the CRF. A participant's parent(s)/legal guardian(s) will be prompted to contact the investigator if the participant experiences a fever  $> 40.0^{\circ}\text{C}$  within the 7 days following vaccination to assess the fever and perform an unscheduled assessment, as applicable (see [Section 8.11.7](#)). Study staff may also contact the participant's parent(s)/legal guardian(s) to obtain additional information if a temperature of  $> 38.9^{\circ}\text{C}$  is entered into an e-diary. Temperature will be measured and recorded to 1 decimal place and then grouped into ranges for the analysis; see [Table 4](#).

**Table 4. Ranges for Fever for the E-diary**

≥37.5°C to 38.4°C
>38.4°C to 38.9°C
>38.9°C to 40.0°C
>40.0°C

Note: Fever is defined as axillary temperature ≥37.5°C.

### 8.2.2.3. Use of Antipyretic/Pain Medication

The participant's parent(s)/legal guardian(s) will be asked to record the use of antipyretic/pain medication (yes/no) in the e-diary (in a provisioned device or application on a personal device) in the evening, daily, for 7 days after each dose of investigational product.

### 8.2.3. Clinical Safety Laboratory Assessments

Clinical safety laboratory tests are not required by this protocol.

If laboratory values from non-protocol-specified laboratory assessments performed at the institution's local laboratory require a change in participant management or are considered clinically significant by the investigator (eg, SAE or AE or dose modification), then the results must be recorded in the CRF.

### 8.2.4. Procedures to Monitor Safety

As this study is the first study where 20vPnC is administered subcutaneously and the study participants are infants, a daily enrollment limit of 5 participants will be in place from study start until the study has accumulated safety data for 45 participants through 7 days of follow-up after Dose 1 and these blinded data have been carefully monitored and reviewed by the study team. If there is no safety signal in the first 45 participants after Dose 1, the daily enrollment limit will be removed.

If any safety signal in the first 45 participants after Dose 1 is identified by the study team, these safety data will be reviewed by senior Pfizer personnel not directly involved with the study conduct. The daily limit will continue until the senior Pfizer personnel reviews the safety data and makes recommendations.

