
This study is the first study that 20vPnC will be administered subcutaneously and the study participants are infants.
	
The 20vPnC investigational product contains the same components and excipients as 13vPnC, and also contains the polysaccharide conjugates for the 7 additional pneumococcal serotypes. Thus, the AE profile of 20vPnC is expected to be similar to 13vPnC, but AEs may be different with the investigational 20vPnC.
 
In a clinical study of 13vPnC administered by SC injection in Japan, local reactions at the 13vPnC injection site (SC injection), particularly redness
	
Daily enrollment will be limited initially with enhanced monitoring of the safety and tolerability of the study vaccine after Dose 1. If there are no unexpected safety concerns after Dose 1 in the first 45 participants, the daily enrollment limit will be removed. Ongoing regular monitoring and review of safety and tolerability of the blinded study data by the study team.

Potential Risk of Clinical Significance	Summary of Data/Rationale for Risk	Mitigation Strategy
20vPnC and 13vPnC		
	
and swelling, occurred at somewhat higher rates compared with studies that administered 13vPnC by IM injection. However local reactions in the study were generally mild or moderate, consistent with other published studies of 13vPnC.
 
In another clinical study of 13vPnC administered by SC injection in Japan, local reactions, particularly redness and swelling, occurred at higher rates at the 13vPnC injection site were comparable with those of 7vPnC administered by SC injection.
	
Study Procedures		

Risks that may be associated with study procedures include risks from blood sample collection, including pain, swelling, bruising, and infection where blood is taken.
	
Risks and possible discomforts from the study procedures such as pain, swelling, bruising, infection around the vein where the child's blood is collected may also occur, although this is very uncommon.
	
The volume and frequency of blood sample collection required during the study has been minimized as far as possible.

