As this study is the first study where 20vPnC is administered subcutaneously and the study participants are infants, a daily enrollment limit of  $\leq 5$  participants will be in place from study start until the study has accumulated safety data from 45 participants through 7 days of follow up after Dose 1. These data will be carefully monitored and reviewed by the study team. If there are no safety signals in the first 45 participants after Dose 1, the daily enrollment limit will be removed (see [Section 8.2.4](#)).

Participants will return to the site for Visit 2 (4 to 8 weeks after Visit 1) and Visit 3 (4 to 8 weeks after Visit 2); they will be assessed for continued eligibility and information will be collected from the participants' parent(s)/legal guardian(s) on AEs, including nonserious AEs, SAEs, NDCMCs, and e-diary follow-up (as needed). Concomitant medications used to treat SAEs or NDCMCs will be recorded.

Information on vaccines administered since the last visit will also be recorded. Participants with continued eligibility will be administered Dose 2 (Visit 2) and Dose 3 (Visit 3). Consistent with the vaccination schedule recommended by the Japan Pediatric Society, specific vaccines containing Hib, Hep B, rotavirus, diphtheria, tetanus, acellular pertussis, and poliovirus antigens will also be administered concomitantly with Doses 2 and 3 (apart from HepB vaccine which is not given with Dose 3) in the upper arm(s) or orally (in the case of rotavirus vaccine). Participants will be observed for 30 minutes after vaccination. Participant's parent(s)/legal guardian(s) will be instructed as in Visit 1.

Participants will return to the site for Visit 4, approximately 1 month (28 to 42 days) after Visit 3. Information will be collected from the participants' parent(s)/legal guardian(s) on AEs, SAEs, NDCMCs, and e-diary follow-up (as needed). Concomitant medications used to treat SAEs or NDCMCs will be recorded. Information on vaccines administered since the last visit will also be recorded. A blood sample will be collected for immunogenicity assessment.

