### **6.3. Measures to Minimize Bias: Randomization and Blinding**

#### **6.3.1. Allocation to Study Intervention**

Participants will be randomized equally to one of the following vaccine groups: (1) 20vPnC SC group, (2) 13vPnC SC group (control vaccine), or (3) 20vPnC IM group.

Allocation of participants to vaccine groups will proceed through the use of an IRT system (IWR). The site personnel (study coordinator or specified designee; either blinded or unblinded) will be required to enter or select information including but not limited to the user's ID and password, the protocol number, and the participant number. The site personnel will then be provided with a vaccine assignment, randomization number, and DU or container number when study intervention is being supplied via the IRT system. The IRT system will provide a confirmation report containing the participant number, randomization number, and DU or container number assigned. The confirmation report must be stored in the site files.

Study intervention will be dispensed at the study visits summarized in the [SoA](#).

Returned study intervention must not be redispensed to the participants.

An otherwise uninvolved third party (unblinded site staff) will be responsible for administration of the study intervention. This includes ensuring that there are no differences in time or effort taken to administer the study intervention and no blinded site staff or participant's parent(s)/legal guardian(s) are able to view the administration (refer to SRM for details).

The study-specific IRT reference manual and IP manual will provide the contact information and further details on the use of the IRT system.

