### **6.3.3. Blinding of the Sponsor**

Those study team members who are involved in ensuring that protocol requirements for study intervention handling, allocation, and administration are fulfilled at the site (eg, study manager; CRAs and unblinded medical monitor) will be unblinded for the duration of the study. All other study team members and all laboratory personnel performing the serology assays will remain blinded to vaccine assigned/received throughout the study.

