## 7.2. Analysis Timings

Statistical analyses are planned to be carried out when the data for the final analyses are available:

- Final analysis: complete safety and immunogenicity data through 1 month after Dose 4 from all participants

For the safety data review for the first 45 participants, listings for demographic characteristics, medical history, nonstudy vaccines, and local reactions/systemic events/AEs through 7 days of follow-up after Dose 1 will be generated.

The study team will remain blinded up to the final analysis.

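### The first-45 safety review was set up for first subcutaneous use of 20vPnC, but it is blinded and covers all three arms, so about 15 of the 45 are expected to be in that arm and a raised rate of common reactions there is hard to see

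*Protocol*

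**What the plan says.** Protocol 4.1 introduces the enrollment limit with its reason: "As this study is the first study where 20vPnC is administered subcutaneously and the study participants are infants". Section 8.2.4 repeats the reason and sets the size of the limit: "a daily enrollment limit of 5 participants will be in place". Two conditions govern its removal. The first is that 45 infants have safety data covering the week that follows their first dose. The second is that "these blinded data have been carefully monitored and reviewed by the study team". If no safety signal is found, the limit is removed. If one is found, senior sponsor personnel outside the study's conduct review the data, and the limit stays until they advise. SAP 2.2 repeats the arrangement.

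The 45 are not tied to an arm. Protocol 6.3.1 states: "Participants will be randomized equally to one of the following vaccine groups", namely 20vPnC SC, 13vPnC SC and 20vPnC IM. SAP 7.2 provides listings for this review (demographics, medical history, nonstudy vaccines, reactions and AEs) and adds: "The study team will remain blinded up to the final analysis". The visible text gives no minimum number per arm, no by-group reading and no definition of a safety signal.

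Two other places bear on the point. The risk table in Protocol 2.3.1 reports that, with 13vPnC given SC in Japan, local reactions, particularly redness and swelling, "occurred at somewhat higher rates compared with studies that administered 13vPnC by IM injection". Section 6.3.3 lists sponsor roles that are not blinded, ending with "CRAs and unblinded medical monitor) will be unblinded for the duration of the study". It ties those roles to intervention handling, allocation and administration, and gives them no part in the first-45 review.

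**The concern.** The review is meant to give early reassurance about a new combination of product and route. About two thirds of the infants in it receive something else: 13vPnC SC, which is the indicated use in Japan, or 20vPnC IM, which Phase 2 studied in US infants. The reviewers cannot tell which infants are which.

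This matters most for the risk that the protocol itself names. Redness and swelling are common and occur in every arm. Blinded, an excess in the SC arm of 20vPnC shows only as a somewhat higher overall count. If the IM arm reacts less than the SC arms, as the risk table suggests, it lowers that count further. The daily limit could then be lifted on a review poorly placed to see the effect it was created to look for.

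**Working it through.** **Inputs.** From the documents: 45 infants, 7 days after Dose 1, blinded review (Protocol 8.2.4); equal allocation to three arms (6.3.1); participant-level listings (SAP 7.2). All reaction rates below are assumptions, because the documents give none.

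**The plan's own figure.** Protocol Table 7 gives the chance of at least one event with N=222. The formula 1 − (1 − p)^n gives 67.1%, 89.3% and 96.5% at p = 0.5%, 1.0% and 1.5%, against 67%, 89% and 97% in the table. It reproduces. The plan has no such calculation for the first 45.

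**Expected size of the arm of interest.** 45 × 1/3 = 15. Under simple randomization the SD is √(45 × 1/3 × 2/3) = 3.2 and the 95% range is 9 to 21; blocking would narrow it. With 15 infants, the chance of at least one SC event is 14% at a true rate of 1%, 54% at 5% and 79% at 10%.

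**Loss from pooling.** Let the other two arms have background rate b and the SC arm b + d. The pooled rate is b + d/3.

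- By group: z = d / √(b(1−b)/15)
- Pooled: z = (d/3) / √(b(1−b)/45)
- Ratio of pooled to by-group: (1/3) × √(45/15) = 0.58, a loss of about 1.7-fold

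The excess shrinks three-fold, but the pooled sample is three times larger, which recovers part of the loss.

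**Exact detection.** For each assumed background, take the smallest count whose false-alarm probability is at most 5%, from Binomial(15, b) or Binomial(45, b). By-group detection comes from Binomial(15, SC rate). Pooled detection comes from the sum of Binomial(15, SC rate) and Binomial(30, b).

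| Background | SC rate | Pooled rate | By-group flag (false alarm) | Detects | Pooled flag (false alarm) | Detects |
|---|---|---|---|---|---|---|
| 30% | 60% | 40.0% | ≥9 of 15 (1.5%) | 61% | ≥20 of 45 (2.8%) | 31% |
| 10% | 30% | 16.7% | ≥5 of 15 (1.3%) | 48% | ≥9 of 45 (3.2%) | 33% |
| 5% | 15% | 8.3% | ≥3 of 15 (3.6%) | 40% | ≥6 of 45 (2.4%) | 17% |
| 2% | 15% | 6.3% | ≥2 of 15 (3.5%) | 68% | ≥4 of 45 (1.2%) | 32% |
| 0.5% | 15% | 5.3% | ≥2 of 15 (0.3%) | 68% | ≥2 of 45 (2.1%) | 71% |

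Counts are discrete, so false-alarm levels are not equal within a row. In the first two rows the pooled flag has the looser level and still detects less. In the fourth row, loosening the pooled flag to ≥3 of 45 raises detection to 56%, at a false-alarm rate of 6.1%. In the last row by-group reading gains no detection, only fewer false alarms.

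**Events with almost no background.** Every case is visible in the listings whether or not the reviewer is blinded. At a 1% SC rate the chance of at least one case is 14% either way; only its arm is unknown.

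**The case against.** Blinded early review is a legitimate choice that protects trial integrity, and the consequence here is limited. The review lifts only a limit of 5 a day; no pause at 45 is described. Other safety steps continue: ongoing review of blinded data (Protocol 2.3.1), frequent e-diary review (8.2.1), immediate notification of Grade 4 reactions (8.2.2) and SAE reporting within 24 hours (8.3.1.1). Escalation to senior personnel is available, and 8.2.4 does not say that they are blinded. The rates and flags in the table are assumed. The medical monitor's described function is not comparative safety review. All of this stands and limits the weight of the point. It does not supply the missing view: continuing review by the study team is also blinded, and escalation starts only after the blinded team has seen a signal.

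A reader might also infer more than the documents support:

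- *That detectability falls three-fold.* Only the excess in the pooled rate does; the loss in z is about 1.7-fold.
- *That only 15 infants say anything about 20vPnC.* That holds for the SC route. For an effect of 20vPnC regardless of route, about 30 of the 45 are informative, and Japanese infants are themselves new to the product: the earlier data in Protocol 2.2.1 are from US infants and Japanese adults.
- *That by-group reading would raise the chance of seeing an SC event from 54% to 90% at a 5% rate.* The 90% belongs to 45 SC infants. By-group reading adds no infants, so 54% is unchanged; what it adds is attribution.
- *That this is the plan's only prospective safety step.* Other steps are listed above, and part of the risk-mitigation text is redacted.

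**Conclusion.** The point holds for common reactions with a background rate. The review is expected to contain about 15 infants given 20vPnC SC, and its blinded form makes an excess in them hard to recognize. Under the assumed rates of 2% to 30% in the other arms, by-group reading detects the excess 40% to 68% of the time, against 17% to 33% pooled. With background near zero the detection advantage disappears. The size rests on assumed rates, on equal background in the two comparison arms and on an expected count of 15. The plan should make this change because it is cheap and the review was created for this arm; it is not a flaw that undermines participant protection as a whole.

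**What to change.** In Protocol 8.2.4 and SAP 7.2, add a reading of the same first-45 listings by vaccine group, done by the medical monitor who is already unblinded under 6.3.3. The monitor returns only 'no concern' or 'refer to the senior personnel' and records how many of the 45 received 20vPnC SC. Removal of the daily limit then follows both this reading and the blinded team's review. The study team and site observers stay blinded, as SAP 7.2 requires.

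The cost is wording in two documents and one set of listings from an unblinded programmer or statistician, with no extra infants or visits. The downside is a new duty for an existing role: one unblinded person sees early by-group safety data, though no immunogenicity data, so 6.3.3 should name the task.
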